1.2.1 Treatment Assignment and Blinding

This is a Phase III, randomized, double-blind, placebo-controlled multicenter study. After written informed consent has been obtained and eligibility has been established, the study site will obtain the patient's identification number and treatment assignment from the interactive voice or web-based response system (IxRS).

Patients will be randomized to one of two treatment arms:

- Arm A: tiragolumab + atezolizumab + CE
- Arm B: placebo + atezolizumab + CE

Randomization will occur in a 1:1 ratio through use of a permuted-block randomization method to ensure that an approximately equal number of patients will be enrolled in

each treatment arm within the baseline characteristics of the following stratification factors:

- ECOG Performance Status (0 vs. 1)
- LDH (\leq ULN vs. $>$ ULN)

Patients should receive their first dose of study drug on the day of randomization if possible. If this is not possible, the first dose should occur within 5 days after randomization.

Study site personnel (with the exception of the unblinded pharmacist) and patients will be blinded to treatment assignment during the study. The Sponsor and its agents will also be blinded to treatment assignment, with the exception of individuals who require access to patient treatment assignments to fulfill their job roles during a clinical trial. These roles include the unblinding group responsible, clinical supply chain managers, sample handling staff, operational assay group personnel, IxRS service provider, and Independent Data Monitoring Committee (iDMC) members.

1.2.2 Data Monitoring

An iDMC will be used to evaluate safety during the study. The safety review of unblinded data by the iDMC will occur approximately every 6 months. The safety data will include disposition, demographic data, adverse events, serious adverse events, and relevant laboratory data.

The Sponsor will remain blinded to the efficacy results until the primary progression-free survival (PFS) analysis. All summaries and analyses by treatment arm for the iDMC reviews will be prepared by an external independent Data Coordinating Center (iDCC). Following the data review, the iDMC will provide a recommendation as to whether the study may continue, whether amendment(s) to the protocol should be implemented, or whether the study should be stopped. The final decision will rest with the Sponsor, taking into consideration the iDMC's recommendation.

Members of the iDMC will be external to the Sponsor and will follow a separate iDMC Charter that outlines their roles and responsibilities, as well as a detailed monitoring plan.

Any outcomes of these safety reviews that affect study conduct will be communicated in a timely manner to the investigators for notification of the sites' Institutional Review Boards/Ethics Committees (IRBs/ECs).

2. STATISTICAL HYPOTHESES

The emphasis of efficacy analyses is to assess whether the treatment benefit in Chinese patients is consistent with the results observed in the global GO41767 study. The study is not powered to demonstrate statistical significance in terms of efficacy, and no formal

hypothesis testing will be performed. Thus, the hypothesis testing is considered exploratory in this bridging study.

3. SAMPLE SIZE DETERMINATION

Approximately 128 patients, including approximately █ patients without presence or history of brain metastases at baseline, are planned for enrollment.

3.1 Co-Primary Endpoint: Progression-Free Survival in the Primary Analysis Set

The primary analysis of the co-primary endpoint of PFS will be conducted at the time of the OS primary analysis. The analyses are expected to occur at approximately █ months after the first patient is randomly assigned, with the assumptions on accrual over a period of approximately 13 months. At the time of the primary analysis of PFS, it is estimated that approximately █ PFS events (██████████) would have been observed in the PAS; the exact number of PFS events will be determined at the time of OS primary analysis.

- PFS curve following one-piece exponential distributions
- Median PFS of █ months in Arm A and █ months Arm B, corresponding to a target hazard ratio (HR) of █
- Dropout rate of █ over 12 months for PFS

3.2 Co-Primary Endpoint: Overall Survival in the Primary Analysis Set

- OS curve following one-piece exponential distributions
- Median OS of [REDACTED] months for Arm A and [REDACTED] months for Arm B, corresponding to a target HR of [REDACTED]
- Dropout rate of [REDACTED] over 24 months for OS

4. ANALYSIS SETS

The analysis sets used for the analyses are defined in the [Table 5](#) below:

Table 5 Analysis Sets

Analysis set	Definition
Full analysis set (FAS)	All randomized patients, whether or not the patient received the assigned treatment
Primary analysis set (PAS)	All randomized patients without presence or history of brain metastases at baseline
Safety evaluable set	All randomized patients who received at least one dose of study treatment
Atezolizumab PK-evaluable set	All patients who received at least one dose of atezolizumab treatment and who have at least one post-baseline PK sample available
Tiragolumab PK-evaluable set	All patients who received at least one dose of tiragolumab treatment and who have at least one post-baseline PK sample available

Tiragolumab ADA-evaluable set	All patients who received at least one dose of tiragolumab treatment and with an ADA assay result from at least one sample result
----------------------------------	---

ADA=anti-drug antibody; FAS=full analysis set; PAS=primary analysis set;
PK=pharmacokinetic.

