6.7 IMMUNOGENICITY ANALYSES

The immunogenicity analyses will include patients with any ADA assessments, with patients grouped according to treatment received.

The numbers and proportions of treatment-emergent ADA-positive patients and ADA-negative patients during both the treatment and follow-up periods for tiragolumab will be summarized by treatment arm.

The relationship between ADA status and safety, efficacy, and PK endpoints may be analyzed and reported via descriptive statistics.

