5. STATISTICAL ANALYSES

The analyses described in this SAP will supersede those specified in Protocol YO42373 for the purposes of a regulatory filing.

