5.7.4 Immunogenicity Analyses

The immunogenicity analyses will include patients with any tiragolumab anti-drug antibody (ADA) assessments, with patients grouped according to the treatment received.

The number and proportion of treatment-emergent tiragolumab ADA-positive patients will be summarized for the Tira+ACE arm..

Demographic and baseline characteristics, PK, efficacy, and safety by treatment-emergent tiragolumab ADA subgroups may be reported.

Immunogenicity analyses will be conducted on the tiragolumab ADA-evaluable sets.

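### The tiragolumab ADA-evaluable set has no post-baseline condition, so treated patients with only a baseline result dilute the treatment-emergent ADA proportion

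*SAP*

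**What the plan says.** SAP Section 4, Table 5, gives one ADA set: "All patients who received at least one dose of tiragolumab treatment and with an ADA assay result from at least one sample result". The two PK sets in the same table are worded differently. The tiragolumab PK set is "All patients who received at least one dose of tiragolumab treatment and who have at least one post-baseline PK sample available", and the atezolizumab PK set is "All patients who received at least one dose of atezolizumab treatment and who have at least one post-baseline PK sample available".

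SAP Section 5.7.4 opens with an inclusion rule: "The immunogenicity analyses will include patients with any tiragolumab anti-drug antibody (ADA) assessments, with patients grouped according to the treatment received". It then names the statistic: "The number and proportion of treatment-emergent tiragolumab ADA-positive patients will be summarized for the Tira+ACE arm". It closes by naming the population: "Immunogenicity analyses will be conducted on the tiragolumab ADA-evaluable sets". No other denominator is given in either document.

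Protocol Section 6.7 opens with the same rule, admitting anyone with any ADA assessment. It plans summaries of "treatment-emergent ADA-positive patients and ADA-negative patients during both the treatment and follow-up periods".

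Two further facts matter. Protocol Section 4.2.2 has the Cycle 1, Day 1 pre-infusion sample assayed in every patient of both arms. Protocol Section 2.4 and SAP Table 1 list two immunogenicity quantities: prevalence at baseline and incidence on study.

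**The concern.** A treatment-emergent finding needs a sample taken after treatment has begun. Because baseline samples are assayed in everyone, almost any patient given tiragolumab qualifies for the ADA set on the baseline sample alone. The set as written is therefore close to all tiragolumab-treated patients, not those in whom a treatment-emergent ADA could be observed.

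A patient who dies, withdraws or misses sampling before the first post-dose ADA sample is then counted in the same way as a patient who was tested and stayed negative. At stake is a listed secondary endpoint, the incidence of ADAs to tiragolumab. It would be understated relative to the proportion among patients who were actually tested after dosing, and a confidence interval around the diluted figure would not reveal this.

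**Working it through.** The documents state no ADA rate, no expected size for the ADA set and no expected number of baseline-only patients, so there is no planned figure to reproduce. What can be checked is the arithmetic of the denominator.

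**Inputs**
- N, patients in the ADA set as written. Protocol Sections 6.1 and 4.2.1 give about 128 patients randomized 1:1, so 128 / 2 = 64 in Arm A. This assumes that all 64 receive tiragolumab and have at least one ADA result.
- k, patients in the set with a baseline result only. Not given; varied below.
- x, treatment-emergent positives. Not given; assumed below.

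**Formula**
- As written: x / N.
- Among patients with a post-baseline result: x / (N - k).
- Ratio of the first to the second: (N - k) / N = 1 - k/N.

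The relative understatement is therefore k/N whatever x is. It is zero when k = 0.

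**Illustration with N = 64 and x = 12 (both assumed)**

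| k | k/N | As written | Post-baseline denominator |
|---|---|---|---|
| 0 | 0% | 12/64 = 18.8% | 12/64 = 18.8% |
| 3 | 4.7% | 12/64 = 18.8% | 12/61 = 19.7% |
| 6 | 9.4% | 12/64 = 18.8% | 12/58 = 20.7% |
| 10 | 15.6% | 12/64 = 18.8% | 12/54 = 22.2% |

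**Gap in percentage points, p × k/N, where p is the proportion among patients with a post-baseline result (N = 64)**

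| p | k = 3 | k = 6 | k = 10 |
|---|---|---|---|
| 10% | 0.5 | 0.9 | 1.6 |
| 20% | 0.9 | 1.9 | 3.1 |
| 30% | 1.4 | 2.8 | 4.7 |

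For scale, the 95% half-width for a 20% proportion at n = 64 is 1.96 × sqrt(0.20 × 0.80 / 64) = 9.8 points.

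**The other route into the set.** The any-sample rule also admits a treated patient with a post-baseline result but no baseline result. SAP Section 5.6.2 defines treatment-emergent for adverse events, and neither document defines it for ADAs. If such a patient is positive and is counted, an antibody that was already present could be scored as treatment-emergent, which would raise x. Baseline assay in all patients should keep this group small, but no figure is given.

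**The case against.** **One set may be meant to serve two endpoints.** Baseline prevalence does need patients with only a baseline result, so an any-sample rule has a legitimate use. That stands as a reason to keep those patients for prevalence, but not as a reason to use them for incidence. The set does not suit prevalence well either: it requires a tiragolumab dose and so leaves out Arm B baseline results, which are assayed, and Section 5.7.4 describes no prevalence summary.

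**The target may be incidence in all treated patients.** The endpoint is worded as incidence during the study. A patient who dies early without forming ADAs is a true non-case under that reading, so calling the figure too low presumes that the target is patients tested after dosing. This partly stands. The formula compares two denominators; it does not show what untested patients would have had. But a patient who was never tested is not known to be negative, and the SAP does not say that it intends to count such patients as negative.

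**Three stronger readings are tempting and are not supported.**
- A reader might infer from "treatment-emergent ADA-positive patients and ADA-negative patients during both the treatment and follow-up periods" that the Protocol intended post-baseline evaluability and that the SAP, which says "The analyses described in this SAP will supersede those specified in Protocol YO42373 for the purposes of a regulatory filing", dropped it. That phrase says when ADA status is counted, not who is evaluable. Protocol Section 6.7 itself starts from any assessment, so it neither repairs the gap nor shows a departure by the SAP.
- A reader might infer that the set definition can only bias the proportion downward. That holds for baseline-only patients. It does not hold for the definition as a whole, because patients without a baseline result could push it up.
- A reader might estimate k from early deaths, using the 12.3-month median survival that Protocol Section 1.2 quotes from another trial. No ADA sampling schedule is visible in the public text, so the time of the first post-dose sample is unknown, and any such range would rest on assumed times.

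**Conclusion.** The concern holds, as a minor point. Table 5 sets no post-baseline condition for the ADA set, Section 5.7.4 uses that set for the treatment-emergent proportion, and Protocol Section 6.7 does not correct it. Each baseline-only patient lowers the reported figure relative to the proportion among patients with a post-baseline result, by a factor of 1 - k/N in total.

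The textual gap and the effect of baseline-only patients are certain. The size is not: k is unknown, and if k = 0 nothing changes. The tables above are illustrations on assumed inputs, and at a 20% rate every gap shown is smaller than the sampling half-width. Immunogenicity is reported descriptively, and PFS and OS are not touched.

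**What to change.** In SAP Table 5, define the population for treatment-emergent ADA incidence as patients with one or more tiragolumab doses and one or more post-baseline tiragolumab ADA results, in line with the PK sets. In Section 5.7.4:
- report the number of tiragolumab-treated patients left out because they have only a baseline result;
- state how a patient with a post-baseline result but no baseline result is classified;
- retain patients with any baseline ADA result as the population for baseline prevalence, and add a sentence that commits to that summary.

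The cost is one condition in Table 5 and a few sentences in Section 5.7.4. No new samples, assays or visits are needed. The incidence denominator falls by k, with a correspondingly slight loss of precision.

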5. STATISTICAL ANALYSES

The analyses described in this SAP will supersede those specified in Protocol YO42373 for the purposes of a regulatory filing.

5.1 GENERAL CONSIDERATION

All efficacy analyses will be performed on the PAS and the full analysis set (FAS), unless otherwise specified. Patients will be analyzed according to the treatment assigned at randomization by IxRS, regardless of whether they receive any assigned study drug.

Safety analyses will be conducted on the safety evaluable set, and will be performed based on the actual treatment patients received. Specifically, a patient will be included in the Tira+ACE arm in the safety analyses if the patient receives any amount of tiragolumab, regardless of the initial treatment assignment at randomization.

Unless otherwise stated, baseline values are the last available data obtained prior to the patient receiving the first dose of study treatment on Cycle 1, Day 1 (or at screening, for patients who were not treated).

5.2 PATIENT DISPOSITION

Study enrollment and reasons for discontinuation from the study will be summarized by treatment arm for the FAS. Study treatment disposition and reasons for discontinuation from study treatment will be summarized for the safety evaluable set.

5.3 PRIMARY ENDPOINTS ANALYSIS

5.3.1 Definition of Co-Primary Endpoints

The co-primary efficacy endpoints are PFS as assessed by the investigator according to RECIST v1.1 and OS in the PAS.

5.3.1.1 **Progression-Free Survival**

The estimand is defined as follows:

- Population: Patients with previously untreated extensive-stage small cell lung cancer without presence or history of brain metastases at baseline
- Variable: Time from randomization to the first documented disease progression as determined by the investigator with the use of RECIST v1.1 or death from any cause, whichever occurs first.

- Treatments:
 - Experimental: tiragolumab + atezolizumab + CE (induction phase; four 21-day cycles) followed by tiragolumab + atezolizumab (maintenance phase; 21-day cycles)
 - Control: placebo + atezolizumab + CE (induction phase; four 21-day cycles) followed by placebo + atezolizumab (maintenance phase; 21-day cycles)
- Intercurrent events:
 - Start of non-protocol anti-cancer therapy (NPT) prior to a PFS event
 - Early discontinuation from study treatment for any reason prior to a PFS event
- Handling of intercurrent events: A treatment-policy with regards to the intercurrent events listed above will be applied for the primary analysis of PFS
- Summary measure: HR for PFS

Patients who have not experienced disease progression and have not died by the data cutoff date will be censored at the date of the last tumor assessment. Patients with no post-baseline tumor assessment will be censored at the date of randomization

5.3.1.2 Overall Survival

The estimand is defined as the follows:

- Population: Patients with previously untreated extensive-stage small cell lung cancer without presence or history of brain metastases at baseline
- Variable: Time from randomization to death from any cause
- Treatments:
 - Experimental: tiragolumab + atezolizumab + CE (induction phase; four 21-day cycles) followed by tiragolumab + atezolizumab (maintenance phase; 21-day cycles)
 - Control: placebo + atezolizumab + CE (induction phase; four 21-day cycles) followed by placebo + atezolizumab (maintenance phase; 21-day cycles)
- Intercurrent events:
 - Start of NPT
 - Early discontinuation from study treatment for any reason
- Handling of intercurrent events: A treatment-policy with regards to the intercurrent events listed above will be applied for the primary analysis of OS
- Summary measure: Hazard ratio for OS

Patients who are not reported as having died by the data cutoff date will be censored at the date when they were last known to be alive. Patients with no post-baseline information will be censored at the date of randomization.

5.3.2 Main Analytical Approach for Primary Endpoints

5.3.3 Handling of Missing Data

Patients who are lost to follow-up will be censored at the last date they were known to be alive for the primary analysis of OS. If >5% of patients are lost to follow-up for OS in either treatment arm, a sensitivity analysis will be performed for the comparisons between two treatment arms in which patients who are lost to follow-up will be considered as having died at the last date they were known to be alive.

5.3.4 Sensitivity Analyses for Primary Endpoints

Sensitivity analyses of the primary endpoints will be performed to assess the impact of stratification. These analyses will follow the same analyses method as the primary endpoints with the exception that PFS and OS will be compared using a stratified log-rank test and the HR will be estimated from stratified Cox regression hazard model according to the protocol-defined stratification factors as entered in IxRS for the PAS (see also Section 5.3.2).

When the clinical effect is delayed by >20% of the median OS of the control group, a sensitivity analysis of OS may be performed using the weighted log-rank test based on the Rho-Gamma weight function family ([Fleming and Harrington, 1991](#)) or piece-wise linear weight functions ([Lin and Leon, 2017](#)) that weight more heavily on late events to account for the delayed clinical effect ([Fine, 2007](#)). In addition, hazard ratio estimates based on the corresponding Cox model ([Lin and Leon, 2017](#)) using the piece-wise linear weight functions may also be provided to enhance clinical interpretation of the treatment effect that varies over time.

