3.1.3 Independent Data Monitoring Committee

An iDMC will be used to evaluate safety during the study. The safety review of unblinded data by the iDMC will occur approximately every 6 months. The safety data will include disposition, demographic data, adverse events, serious adverse events, and relevant laboratory data.

The Sponsor will remain blinded to the efficacy results until the primary PFS analysis. All summaries and analyses by treatment arm for the iDMC reviews will be prepared by an external independent Data Coordinating Center (iDCC). Following the data review, the iDMC will provide a recommendation as to whether the study may continue, whether amendment(s) to the protocol should be implemented, or whether the study should be

stopped. The final decision will rest with the Sponsor, taking into consideration the iDMC's recommendation.

Members of the iDMC will be external to the Sponsor and will follow a separate iDMC Charter that outlines their roles and responsibilities, as well as a detailed monitoring plan.

Any outcomes of these safety reviews that affect study conduct will be communicated in a timely manner to the investigators for notification of the sites' Institutional Review Boards/Ethics Committees (IRBs/ECs).

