6. STATISTICAL CONSIDERATIONS AND ANALYSIS PLAN

This is a Phase III, randomized, double-blind, placebo-controlled, multicenter study designed to evaluate the efficacy and safety of tiragolumab plus atezolizumab and CE compared to placebo plus atezolizumab and CE as 1L treatment in patients with chemotherapy-naïve ES-SCLC. The study is not powered to demonstrate statistical significance in terms of efficacy, and no formal hypothesis testing will be performed. More details of the analyses will be provided in the Statistical Analysis Plan (SAP).

The analyses of PFS and OS will be performed in the PAS and the FAS. Patients will be grouped according to the treatment assigned at randomization, regardless of whether they receive any assigned study drug. Confirmed ORR will be analyzed in patients within the PAS and the FAS who have measurable disease at baseline. DOR will be assessed in patients who have a confirmed objective response in the PAS and the FAS. TTCD analyses, mean scores and mean change from baseline analysis on PROs will be performed in the PAS and the FAS.

Safety analyses will be conducted in all randomized patients who received at least one dose of study treatment. Safety analyses will be performed by treatment arm and will be based on actual treatment received. Specifically, a patient will be included in the tiragolumab plus atezolizumab arm in the safety analyses if the patient receives any amount of tiragolumab, regardless of the initial treatment assignment at randomization.

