6.4.1 Co-Primary Efficacy Endpoints

The co-primary efficacy endpoints are PFS (as assessed by the investigator according to RECIST v1.1) and OS in the PAS.

PFS is defined as the time between the date of randomization and the date of first documented disease progression (as assessed by investigators according to RECIST v1.1) or death, whichever occurs first. Patients who have not experienced disease progression and have not died by the time of analysis will be censored at the time of the last tumor assessment. Patients with no post-baseline tumor assessment will be censored at the date of randomization.

OS is defined as the time between the date of randomization and death from any cause.

Data for patients who are not reported as having died by the date of analysis will be censored at the date when they were last known to be alive. Data for patients who do not have post-baseline information will be censored at the date of randomization.

PFS and OS will be compared between treatment arms with use of the unstratified log-rank test. The HR for PFS and OS will be estimated using both unstratified and stratified Cox proportional hazards model. The 95% CI for the HR will be provided.

[REDACTED]

The investigator-assessed PFS rates at 6 months and at 1 year and OS rates at 1 year, 18 months, and 2 years after randomization will be estimated using Kaplan-Meier methodology for each treatment arm, along with 95% CIs calculated using the standard error derived from Greenwood's formula. The 95% CI for the difference in PFS rates and OS rates between the two treatment arms will be estimated using the normal approximation method.

The timing of the final PFS analysis is described in Section 6.1.1 and the analysis timing for OS is described in Section 6.1.2.

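### SAP 5.3.4 produces the late-weighted OS test and weighted hazard ratio only if a delayed effect is judged present, so these supportive results are selected and tend towards apparent benefit under most readings of the trigger

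*SAP*

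**What the plan says.** SAP 5.3.4 sets a condition, "When the clinical effect is delayed by >20% of the median OS of the control group", under which "a sensitivity analysis of OS may be performed using the weighted log-rank test based on the Rho-Gamma weight function family". Piece-wise linear weights are offered as an alternative. Both are described as weights "that weight more heavily on late events to account for the delayed clinical effect". A hazard ratio from the matching weighted Cox model may be added to help interpretation.

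The readable text gives no rho or gamma, no change points and no rule for choosing between the two families. It does not say how the delay is measured, on which data, or who decides.

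The surrounding text matters here:

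- Protocol 6.4.1 fixes the main comparison: "PFS and OS will be compared between treatment arms with use of the unstratified log-rank test". The Cox hazard ratio is given alongside.
- Protocol section 6 states "The study is not powered to demonstrate statistical significance in terms of efficacy, and no formal hypothesis testing will be performed". SAP section 2 adds "Thus, the hypothesis testing is considered exploratory in this bridging study".
- SAP 3.2 plans OS with an "OS curve following one-piece exponential distributions" and a single target hazard ratio, so no delay is built into the design.
- SAP 5.8.1 plans no interim analysis of PFS or OS. Protocol 3.1.3 states "The Sponsor will remain blinded to the efficacy results until the primary PFS analysis", and SAP 3.1 places that analysis at the time of the primary OS analysis.

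**The concern.** A delay in effect is a property of the two OS curves. With a constant hazard ratio planned and no interim efficacy look, the first realistic chance to judge it is when OS by arm is seen at the primary analysis. The analysis that gives late events more weight would then be produced because late separation had been seen, which uses the same data twice.

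The weighted hazard ratio is affected as well as the p-value. SAP section 2 puts the emphasis on whether benefit in Chinese patients is consistent with the global study, and the SAP's summary measure for OS is the hazard ratio. A weighted hazard ratio that appears only in trials with a favourable late pattern could be read as support for benefit. Calling the testing exploratory does not remove selection from an estimate.

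**Working it through.** **No stated figure to reproduce.** The readable text gives no alpha, power or error rate for the weighted test. The size of the effect was therefore simulated under no treatment effect (HR = 1).

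**Inputs from the documents**
- 128 randomized, 15% with brain metastases (Protocol 6.1): 128 × (1 − 0.15) = 108.8, so about 109 in the PAS
- 1:1 allocation (Protocol 3.1.1)
- 13-month accrual (SAP 3.1)

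**Assumed, because redacted**
- Control median OS of 12.3 months (atezolizumab arm of the earlier phase III trial in Protocol 1.2), and also 15 months
- 65, 80 or 90 deaths in the PAS
- 5% dropout over 24 months
- One-sided reference level of 2.5%

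**Statistic.** With pooled survival S(t−), the Fleming-Harrington weight is w(t) = S(t−)^rho × (1 − S(t−))^gamma. For (0,1) this is w = 1 − S(t−). The test is Z = Σw(O − E) / √(Σw²V), and a false benefit is Z beyond 1.96 in favour of tiragolumab.

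**Trigger.** Let tau be 20% of the observed control median; at a median of 12.3 months, 0.20 × 12.3 = 2.46 months. The SAP does not define the delay, so several readings were tried, with 20,000 null trials per scenario. The last column takes the most favourable of four weights: (0,1), (1,1), (0,0.5) and one piece-wise linear.

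| Reading of a delayed effect | Trigger fires | False benefit given trigger, (0,1) | Same, best of four weights |
|---|---|---|---|
| Estimated HR ≥ 1 before tau, < 1 after | 26–27% | 4.1–4.8% | 5.3–7.0% |
| Curves not separated in favour at tau, separated at control median | 24% | 4.7–5.0% | 6.1–7.3% |
| Last curve crossing after tau, tiragolumab ahead afterwards | 20% | 7.7–9.8% | 9.4–12.9% |
| HR after tau lower than HR before tau | 50% | 3.8–4.1% | 4.9–5.9% |

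Monte Carlo error on the conditional rates is about 0.2 to 0.5 percentage points. A different coding of a curve-crossing trigger gave 3.5–3.9%, so the third row depends strongly on definition.

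**Looser reading.** If the trigger is only that no benefit is visible at tau, separate runs with an assumed cutoff at month 28 gave 2.3–2.4%, so there is no inflation. About 48% of triggered trials then favoured tiragolumab, against 74% under the second row's reading.

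**Always run.** With (0,1) fixed and run in every null trial, the rate was 2.4–2.7% (2.8% in a separate run).

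**Weighted hazard ratio.** A further null simulation (6,000 trials per scenario; 65 or 80 deaths; medians of 12.3 or 15 months) used the first two readings. The piece-wise linear weight was assumed to rise from zero to full effect by 40% of the control median. With a true HR of 1.0:
- over all trials, the median weighted HR was 1.00–1.01
- in triggered trials, the median ordinary HR was 0.91–0.93
- in triggered trials, the median weighted HR was 0.83–0.87, and it was below 1 in 76–91% of them

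**The case against.** **The data source is not stated.** The SAP does not say that the delay is judged from unblinded data in this trial. A delay seen in the global study, to which SAP section 2 ties this one, is conceivable. That is fair: use of this trial's curves is an inference. It is the natural one, because nothing in SAP 5.3.4 points to outside data.

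**No error rate is there to breach.** A reader might infer that the plan loses type I error control. The documents do not support that. They set no level, plan no formal testing, and make this an optional sensitivity analysis. The unweighted log-rank test and Cox hazard ratio are reported regardless, and OS rates at fixed times show a late difference without any trigger. At a two-sided 5% reference, the conditional rate stays between 4.1% and 5.3% in three of the four tabulated readings, although nearly all rejections are in the direction of benefit. This objection stands in full. What remains is selection in a supportive result.

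**The direction is not fixed.** A reader might infer that the weighted analysis favours tiragolumab whenever it is produced. The 48% under the looser reading contradicts that.

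**Either test positive.** A reader might also argue that the trigger raises the chance that at least one of the two tests looks positive. That does not count against the trigger. Triggered rejections are a subset of always-run rejections, so removing the trigger cannot lower this figure. It was 3.3% with the trigger and 3.9% without it. It reflects two correlated tests.

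**Redaction.** Event numbers, medians and dropout are blacked out, and SAP 5.3.2 shows no readable text. The magnitudes are therefore conditional on assumptions. The paragraph with the trigger does read as complete.

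**Conclusion.** The concern holds in a limited form. SAP 5.3.4 states a rule under which a late-weighted OS test and weighted hazard ratio appear only after a delayed effect is judged present, with that judgement undefined and the weights open. If the judgement uses this trial's curves, the supportive results are selected. Under readings that require a better effect later, the one-sided false-benefit rate given the trigger is roughly 4% to 10%, against 2.4% to 2.8% if always run. It can reach 12.9% if the weight is also chosen after seeing the data. Under the looser reading there is no inflation. The spread between readings is itself a consequence of leaving the delay undefined. The primary OS result is untouched and no stated error rate is exceeded. All magnitudes rest on assumed medians, deaths, dropout and cutoff, and on assumed readings of the trigger.

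**What to change.** In SAP 5.3.4, delete the 20% trigger and the permissive *may*. Before unblinding, name one late-weighting function with its parameters. Either of these would do:

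- Fleming-Harrington with rho = 0 and gamma = 1
- one piece-wise linear weight with stated change points, together with its weighted hazard ratio

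State that it will be reported for OS in the PAS whatever the curves look like, labelled descriptive, beside the unweighted log-rank test and Cox hazard ratio. Remove the other weight family.

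Protocol 4.5.6 records the primary-analysis cutoff as 31 August 2023. If OS by arm has already been seen, the report should say when the weight was chosen.

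A restricted mean survival analysis is not needed for this. At an assumed month-28 cutoff with 13-month accrual, only (28 − 24)/13 = 31% of patients could have 24 months of follow-up.

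The cost is a change of wording and one extra supportive output, which is less efficient when hazards are proportional.
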